## TITLE PAGE

Title	Non-interventional post-authorization safety study (PASS) of patients treated with idecabtagene vicleucel (ide-cel, bb2121) for multiple myeloma (MM) in the postmarketing setting		
Protocol version identifier	BB2121-MM-006 (also known as CA089-P11)		
Date of protocol version	24 Nov 2021		
EU PAS register number	To Be Confirmed		
Active substance	idecabtagene vicleucel (ide-cel, bb2121)		
Medicinal product	Abecma®		
Product reference	EU/1/21/1539/001		
Procedure number	EMEA/H/C/004662		
Marketing authorisation holder(s) (MAH)	Bristol-Myers Squibb Pharma EEIG		
Joint PASS	No		
Research question and objectives	
 
Primary Objective
 
To characterize the incidence and severity of selected adverse drug reactions (ADRs), as outlined in the Summary of Product Characteristics (SmPC), in patients treated with ide-cel in the postmarketing setting and to monitor for potential clinically important adverse events (AEs) that have not yet been identified as part of the ide-cel safety profile.
 
Secondary objective
 
To assess survival in patients treated with ide-cel in the postmarketing setting.
 
		

Country(-ies) of study	United States (US); European countries; other countries may	
	be included	
Author		
МАН	Bristol-Myers Squibb Pharma EEIG	
	[name]	
	[name]	
MAH contact person		
real for the second sec		

## 2. LIST OF ABBREVIATIONS

Abbreviation	Definition	
ADAM	Analysis Data Model	
ADR	Adverse drug reaction	
AE	Adverse event	
AESI	Adverse event of special interest	
ALL	Acute lymphoblastic leukemia	
AMT	Antimyeloma therapy	
ASCT	Autologous stem cell transplantation	
auto	Autologous	
BCMA	B-cell maturation antigen	
CAR	Chimeric antigen receptor	
CDISC	Clinical Data Interchange Standards Consortium	
CFR	Code of Federal Regulations	
CI	Confidence interval	
CIBMTR	Center for International Blood and Marrow Transplant Research	
CIC	Center Identification Code	
CLL	Chronic lymphocytic leukemia	
Clopp Pears	Clopper Pearson	
CR	Complete response	
CRF	Case Report Form	
CRID	CIBMTR Research Identification	
CRS	Cytokine release syndrome	
EBMT	European Society for Blood and Marrow Transplantation	
EC	European Commission	
ECOG	Eastern Cooperative Oncology Group	
EMA	European Medicines Agency	
ESMO	European Society for Medical Oncology	
EU	European Union	
FDA	Food and Drug Administration	
FN3	FormsNet3	
GPP	Good Pharmacoepidemiology Practice	

Confidential and Proprietary

Abbreviation	Definition
GVHD	Graft-versus-host disease
НСР	Health care professional
НСТ	Hematopoietic cell transplantation
IARC	International Agency for Research on Cancer
ICF	Informed consent form
IS	Infused Set
IV	Intravenously
КМ	Kaplan-Meier
LDC	Lymphodepleting chemotherapy
LVV	Lentiviral vector
MAA	Marketing Authorization Application
mAbs	Monoclonal antibodies
МАН	Marketing authorisation holder
MDS	Myelodysplastic syndrome
MedDRA	Medical Dictionary for Regulatory Activities
MHA	Master Healthcare Data Agreement
MM	Multiple myeloma
MoA	Mechanism of action
M-protein	Monoclonal protein
NCCN	National Comprehensive Cancer Network
NCI CTCAE	National Cancer Institute Common Terminology Criteria for Adverse Events
NHL	Non-Hodgkin lymphoma
NMSC	Non-melanoma skin cancer
OOS	Out of specification
ORR	Overall response rate
OS	Overall survival
PASS	Post-authorization safety study
PBMCs	Peripheral blood mononuclear cells
Pd	Pomalidomide and dexamethasone
PFS	Progression-free survival
PIs	Proteasome inhibitors

Abbreviation	Definition	
PSUR	Periodic safety update report	
РТ	Preferred term	
PVP	Pharmacovigilance Plan	
Q	Quarter	
RMP	Risk Management Plan	
RNA	Ribonucleic acid	
R/R	Relapsed and/or refractory	
SAP	Statistical analysis plan	
scFv	Single chain variable fragment	
SCT	Stem cell transplantation	
SDTM	Study Data Tabulation Model	
SEER	Surveillance, Epidemiology, and End Results	
SES	Safety and Effectiveness Set	
SmPC	Summary of Product Characteristics	
SOC	System organ class	
SPM	Second primary malignancy	
TLS	Tumor Lysis Syndrome	
UPN	Unique Patient Number	
US	United States	
USA	United States of America	
WHO	World Health Organization	

## 4. ABSTRACT

**Title:** Non-interventional post-authorization safety study (PASS) of patients treated with idecabtagene vicleucel (ide-cel, bb2121) for multiple myeloma (MM) in the postmarketing setting

#### **Rationale and background:**

The purpose of this study is to characterize the safety profile of ide-cel in the postmarketing setting.

This study will include patients from existing independent registries, such as, but not limited to, the European Society for Blood and Marrow Transplantation (EBMT) and the Center for International Blood and Marrow Transplant Research (CIBMTR).

Ide-cel, bb2121 is a genetically modified autologous T cell immunotherapy product consisting of T cells transduced with an anti-BCMA02 chimeric antigen receptor (CAR) lentiviral vector (LVV). Autologous T cells transduced ex vivo with the anti-BCMA02 CAR LVV express the anti-BCMA02 CAR on the T cell surface.

Potential adverse reactions, associated with ide-cel therapy, include cytokine release syndrome (CRS), neurotoxicity, cytopenias, infections, and secondary malignancies.

The BB2121-MM-006 study will be part of the overall ide-cel Risk Management Plan (RMP) including any required regional Pharmacovigilance Plan (PVP) outside the European Union (EU).

#### **Objectives:**

Primary Objective

• To characterize the incidence and severity of selected adverse drug reactions (ADRs), as outlined in the Summary of Product Characteristics (SmPC), in patients treated with ide-cel in the postmarketing setting and to monitor for potential clinically important adverse events that have not yet been identified as part of the ide-cel safety profile.

Secondary Objective

• To assess survival in patients treated with ide-cel in the postmarketing setting.

#### Study design:

This study is designed as a non-interventional cohort study that is part of multiple registries of patients with MM treated with ide-cel therapy in the postmarketing setting which includes patients treated with out of specification (OOS) product.

Data from a total of 1000 patients treated with ide-cel, including a minimum of 300 EU patients, will be collected until death, lost to follow-up, or withdrawal of consent, or up to 15 years, whichever occurs first. This study is expected to require up to 5 years to select the planned 1000 patients.

No comparison groups will be defined, and no inferential testing will be performed.

#### **Study Endpoints**

Incidence and severity of selected adverse drug reactions (ADRs) reported post ide-cel infusion:

#### Primary Safety Endpoint(s)

Incidence and severity of the following adverse events (AEs) reported post ide-cel infusion:

- All secondary malignancies
- Cytokine release syndrome (CRS) Grade  $\geq 3$
- Neurotoxicity Grade  $\geq 3$
- Prolonged cytopenias
- Pregnancy outcome
- Other AEs considered related to ide-cel treatment

#### Secondary Effectiveness Endpoint

- Overall survival (OS)
- Progression-free survival (PFS)

#### **Eligibility Criteria**

All patients who meet the following eligibility criterion will be selected from the registries:

• Patient must have been treated with at least one infusion of ide-cel in the postmarketing setting. Patients treated with OOS product will also be eligible.

#### **Analysis Populations:**

Due to the observational nature of the study, no formal analysis populations such as intent to treat or a per protocol population can be defined. Instead, the term "analysis sets" will be used.

- **Infused Set (IS):** Is defined as all patients selected from the registry and meeting the above-mentioned eligibility criterion, where baseline and disease classification information is available.
- Safety and Effectiveness Set (SES): Is defined as all patients from the IS with information collected at least after 100 days.

#### Data to be collected:

The information recorded will include, but not be limited to, the following variables:

- Demographics (eg, age, sex, height, weight)
- Center where ide-cel treatment was received

- Information on the underlying disease
- Functional status / prognostic characterization (performance status)
- Prior therapy for the underlying disease
- Ide-cel administration
- Survival status
- Ide-cel-related AEs including neurotoxicity, CRS, prolonged cytopenias, and related treatments
- Information on any secondary malignancy
- Pregnancy outcome
- Next treatment(s) for the underlying disease

#### **Study size justification:**

Since this is a single-arm non-interventional cohort study with no comparisons and no statistical hypothesis testing, no formal powered sample size calculation is possible. Instead, based on pragmatic nonstatistical reasons, the approach taken is to use a fixed number of 1000 patients from registries, which is considered feasible within the estimated 5-year selection period. The sample size is justified by reporting the precision of assumed incidences corresponding to certain safety endpoints chosen as examples.

For the chosen sample size of 1000 patients, there would be a 95% chance to observe at least one event if the true incidence rate is equal to or above 0.3 event per year (using normal approximation according to Wald).

To justify the sample size, precision estimates for example incidences, taken from the literature, are provided by calculating exact 95% (Clopper Pearson) confidence intervals (based on a binomial distribution).

Assumed incidences for secondary malignancies were based on second primary malignancies (SPMs) data from Mahindra et al (Mahindra, 2015) and Costa et al (Costa, 2018). The incidences for CRS and neurotoxicity correspond to incidences reported as AEs of special interest (AESIs) by Raje et al (Raje, 2019) based on the CRB-401 trial (ClinicalTrials.Gov#: NCT02658929). The populations from these three sources are characterized as follows:

- **Mahindra et al population**: MM patients with an age range from 22 to 80 years and a first autologous stem cell transplantation (ASCT) within 18 months of MM diagnosis, reported to the CIBMTR between 1990 and 2010.
- **Costa et al population**: Three cohorts of patients with an age range from 19 to 64 years, with MM as first malignant neoplasm, reported to the Surveillance, Epidemiology, and End Results (SEER) between 1995 and 2009.
- **Raje et al population**: MM patients in the United States (US) with an age range from 37 to 75 years and an Eastern Cooperative Oncology Group (ECOG) score of 0 or 1.

Data Source	Description	#	Observed	Incidence	Clopp Pear	s 95% CI
		Patients	Incidence	Proportion	Lower	Upper
(Mahindra, 2015)	overall SPMs (1990-2010)	4161	145	0.035	0.025	0.048
	excluding NMSC, including MDS					
(Costa, 2018)	overall SPMs (1995-2009)	9833	420	0.043	0.031	0.058
	excluding NMSC, excluding MDS					
(Raje, 2019)	$CRS \ge Grade 3$	33	2	0.061	0.047	0.078
(Raje, 2019)	Neurotoxicity $\geq$ Grade 3	33	1	0.030	0.020	0.043

CI = confidence interval; Clopp Pears = Clopper Pearson; CRS = cytokine release syndrome; MDS = myelodysplastic syndrome; NMSC = nonmelanoma skin cancer; SPM = second primary malignancy.

Thus, in conclusion, if similar incidences are observed in this study, this would provide sufficient precision for a meaningful interpretation of the observed incidences.

**Data analysis:** In this cohort study, results will be analyzed and reported descriptively; no formal hypothesis testing is planned.

Confidence intervals will be presented as 2-sided 95% intervals unless specified differently for specific analyses.

Summary statistics will consist of the number and percentage of patients in each category for discrete variables, whereas for continuous variables the sample size, mean, median, standard deviation, minimum, and maximum will be given.

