## 9. **RESEARCH METHODS**

## 9.1. Study Design

This study is designed as a non-interventional cohort study that is part of multiple registries of patients with MM treated with ide-cel in the postmarketing setting which includes patients treated with out of specification (OOS) product.

Data from a total of 1000 patients treated with ide-cel, including a minimum of 300 EU patients, will be collected until death, lost to follow-up, or withdrawal of consent, or up to 15 years, whichever occurs first. This registry study is expected to require up to 5 years to select the planned 1000 patients.

No comparison groups will be defined and no inferential testing will be performed.

Secondary malignancies must be reported to the Sponsor by the treating physicians in order to expedite AE reporting. In the event that a secondary malignancy of T cell origin is suspected, the Sponsor should be contacted to obtain instructions on the collection and transfer of a tumor tissue sample for testing in a separate process, outside of this PASS. In the postmarketing setting, the Sponsor will offer transgene assay service testing for all secondary malignancies of suspected T cell origin where a sample is available, as a routine pharmacovigilance measure to ensure gathering the most information possible for clinical assessment of the reported spontaneous case.

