## 9.5. Study Size

Since this is a single-arm noninterventional cohort study with no comparisons, no statistical hypothesis testing and no formal powered sample size calculation is possible. Instead, a fixed number of 1000 patients from registries is used based on pragmatic non statistical reasons, which is considered feasible within the estimated 5-year selection period. The study size is justified by providing precision estimates (see below).

For the chosen sample size of 1000 patients, in general there would be a 95% chance to observe at least one event if the true incidence is  $\geq 0.3$  events per year (using normal approximation according to Wald).

To justify the sample size, precision estimates for example incidences, taken from the literature, are provided by calculating exact 95% Clopper Pearson confidence intervals (based on a binomial distribution). (see table below).

Assumed incidences for secondary malignancies were based on SPMs data from Mahindra and co-workers (Mahindra, 2015) and Costa and co-workers (Costa, 2018). The incidences for CRS and neurotoxicity correspond to incidences reported as AEs of special interest (AESIs) by Raje and co-workers (Raje, 2019) based on the CRB-401 trial (ClinicalTrials.Gov#: NCT02658929). The populations from these three sources are characterized as follows:

- **Mahindra et al population**: MM patients with an age range from 22 to 80 years and a first autologous stem cell transplantation (auto SCT) within 18 months of MM diagnosis, reported to the CIBMTR between 1990 and 2010.
- **Costa et al population**: Three cohorts of patients with an age range from 19 to 64 years, with MM as first malignant neoplasm, reported to the SEER between 1995 and 2009.
- **Raje et al population**: MM patients in the US with an age range from 37 to 75 years and an Eastern Cooperative Oncology Group (ECOG) score of 0 or 1.

Data Source	Description	Observed I		Incidence	Clopp Pea	ars 95% CI
		Patients	Incidence	Proportion	lower	upper
					(for 1000 j	patients)
(Mahindra, 2015)	overall SPMs (1990-2010)	4161	145	0.035	0.025	0.048
	excluding NMSC, including MDS					
(Costa, 2018)	overall SPMs (1995-2009)	9833	420	0.043	0.031	0.058
	excluding NMSC, excluding MDS					
(Raje, 2019)	$CRS \ge Grade 3$	33	2	0.061	0.047	0.078
(Raje, 2019)	Neurotoxicity $\geq$ Grade 3	33	1	0.030	0.020	0.043

Table 5:	Assumed	Incidence	for S	Safety	Endpoints
----------	---------	-----------	-------	--------	-----------

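### The detectable-incidence sentence gives 0.3 events per year where 1000 patients and a 95% chance give about 0.003 (0.3%)

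*Protocol*

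**What the plan says.** The sentence appears twice in the protocol. The Abstract, under study size justification, says that the chosen 1000 patients would give a "95% chance to observe at least one event if the true incidence rate is equal to or above 0.3 event per year", and names the method as "using normal approximation according to Wald". Section 9.5 repeats the threshold as at least 0.3 "events per year (using normal approximation according to Wald".

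Neither place gives a percent sign, a denominator (per patient, per 100 patients, per patient-year) or an observation period for this figure. Section 9.1 says that data "will be collected until death, lost to follow-up, or withdrawal of consent, or up to 15 years, whichever occurs first".

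Both places also say that 1000 was chosen for practical rather than statistical reasons, and that the size is justified by precision. For four example incidences, precision estimates "are provided by calculating exact 95% Clopper Pearson confidence intervals (based on a binomial distribution" (Table 5). Those incidences are proportions between 0.030 and 0.061.

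**The concern.** A 95% chance of seeing at least one event fixes the threshold incidence once the number of patients is known. For 1000 patients that threshold is a few per thousand, whereas the protocol gives three tenths. The sentence also sits badly beside Table 5, where every example incidence is five to ten times smaller than 0.3.

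Part of the primary objective is to monitor for clinically important adverse events not yet in the safety profile. This sentence is the only place where the protocol says how uncommon an event can be and still be likely to appear. Table 5 deals with something else: the precision for known events at 3% to 6%. A reader who wants the detection limit of a study that belongs to the Risk Management Plan gets the wrong number from the Abstract and the same wrong number from the body.

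**Working it through.** **Inputs.** n = 1000 patients and a 95% chance of at least one event; stated threshold 0.3 per year; named method, the Wald normal approximation (Abstract and Section 9.5).

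**Step 1: try to reproduce the stated figure.**

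- *Per patient, over one year.* Expected events are 1000 × 0.3 = 300. The chance of at least one is 1 − (1 − 0.3)^1000, which is 1.000 to machine precision, not 0.95. At an incidence of 0.3, 95% needs only ln(0.05)/ln(0.7) = 8.4, so 9 patients, or −ln(0.05)/0.3 = 10 patient-years.
- *Whole cohort, 0.3 events per year in total.* The chance over T years is 1 − exp(−0.3T):

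| T (years) | Chance of at least one event |
|---|---|
| 1 | 25.9% |
| 5 | 77.7% |
| 10 | 95.0% |
| 15 | 98.9% |

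This reading gives 95% only at ten years. The same holds for 0.3 per 1000 patient-years with all 1000 patients followed throughout.

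No reading that the text supports returns 0.3.

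**Step 2: solve for the threshold.**

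- Exact binomial: 1 − (1 − p)^1000 = 0.95, so p = 1 − 0.05^(1/1000) = 0.00299.
- Poisson: p = −ln(0.05)/1000 = 0.0030.
- Forward check at p = 0.003: 1 − 0.997^1000 = 0.9504.

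The ratio of stated to derived is 0.3/0.003 = 100.

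**Step 3: the Wald reference.** The smallest p whose Wald lower limit exceeds zero is p = z²/(n + z²).

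| Version | z | Threshold p | Chance of at least one event, 1 − (1 − p)^1000 |
|---|---|---|---|
| One-sided | 1.645 | 0.0027 (0.27%) | about 93% |
| Two-sided | 1.96 | 0.0038 (0.38%) | about 98% |

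One-sided Wald rounds to 0.3%, so it may be where the digit came from. It answers a different question, though: neither version gives a 95% chance of at least one event.

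**Step 4: the unit.** The binomial result is a proportion of patients over whatever period they are observed. It becomes a yearly rate only when person-time is stated. With 1000 patient-years, 0.3 per 100 patient-years gives 1 − exp(−0.003 × 1000) = 0.9502. If all 1000 patients were followed for 5 years, the threshold rate would be −ln(0.05)/5000 = 0.0006 per patient-year; for 10 years it would be 0.0003.

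**Step 5: the neighbouring table.** Clopper-Pearson limits for n = 1000:

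| Events | Recomputed | Table 5 |
|---|---|---|
| 35 | 0.024 to 0.048 | 0.025 to 0.048 |
| 43 | 0.031 to 0.057 | 0.031 to 0.058 |
| 61 | 0.047 to 0.078 | 0.047 to 0.078 |
| 30 | 0.020 to 0.043 | 0.020 to 0.043 |

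The table agrees to within about 0.001.

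**The case against.** The strongest defence is that little depends on the sentence. The sample size was set pragmatically, the stated justification is the precision table, and that table holds up. This stands. A reader might infer that the case for 1000 patients collapses, but the documents do not support that, and no endpoint or analysis uses the 0.3.

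A second defence is that the digit is right and only a unit is missing, so the factor of 100 depends on supplying a per-patient-year denominator. This also stands in part: a lost percent sign or per-100 denominator is the likeliest cause, and the factor of 100 belongs to that one reading. But the whole-cohort reading fails as well, and the text offers no third. An artefact of text extraction is unlikely, because the figure appears in two places and the 95% in both sentences kept its percent sign.

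Third, the sentence is literally true as a sufficient condition, since any incidence of 0.3 or more gives better than a 95% chance. That does not rescue it, because its purpose is to state the threshold.

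Fourth, a reader might conclude that the named Wald method cannot have produced the figure. That goes too far: one-sided Wald gives 0.27%, which rounds to 0.3%. What remains is that Wald uses a different criterion and that its sidedness is not stated.

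Finally, a reader might take the study to be able to detect only events that strike about one patient in three each year. That is merely what the sentence says if read literally; Table 5, directly below it, makes plain that much smaller incidences can be studied.

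**Conclusion.** The sentence is wrong as written in both places. For 1000 patients and a 95% chance of at least one event, the threshold is about 0.003, or 3 per 1000 patients. The stated 0.3 is 100 times that if read per patient-year, and needs an unstated ten-year period if read for the whole cohort.

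The derived value assumes independent patients, all 1000 contributing to the observed period, and every event captured. It is a proportion over that period, and becomes 0.3 per 100 patient-years only if 1000 patient-years are observed.

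This is a misstated property of the design, comparable to a wrongly stated power, and it should be corrected. It does not affect the sample size, the precision table or the planned analyses.

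**What to change.** Correct the sentence identically in the Abstract and in Section 9.5, in one of two ways:

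- As a proportion: with 1000 patients there is a 95% chance of observing at least one patient with an event whose true incidence is 0.3% (3 per 1000 patients) or more over the observed period, by exact binomial.
- As a rate, if that is what is meant: 0.3 per 100 patient-years, given 1000 patient-years of observation (Poisson).

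In either case drop the Wald reference, since the exact binomial or Poisson calculation gives the stated 95% directly.

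An optional addition, which corrects no existing claim, is the matching value for the minimum of 300 EU patients: 1 − 0.05^(1/300) = 0.0099, or about 1.0%.

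The cost is two sentences at the next protocol amendment, with no change to design, data collection or analysis.

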#### Milestones:

- Date of Initial Registry Protocol Submission to EMA as part of Marketing Authorisation Application: 30 Apr 2020
- Date of Final Registry Protocol Approval from EMA: Quarter (Q)4 2021
- Start of data collectiona: Q1 2022
- Registration in the EU PAS register: TBC
- Study Progress Updates: Per the periodic safety update report (PSUR) cycle, according to the EU reference dates (EURD) list
- Safety reports: Every 6 months (aligned with the reporting period of the PSUR)b. Additional reports every 3 months if a new safety concern is identified
- Interim reportsc: At year 5, 10 and 15 or when last patient is out of the registry-based study
- Date of Study Completiond: Q1 2042
- Date of Final Study Report Submission to EMA: Q1 2043

<sup>a As the data collection in the EBMT Registry is independent of this study (secondary use of data), the start of data collection corresponds to the date from which data extraction starts. First data extraction for study BB2121-MM-006 will take place three months after protocol approval from EMA.

- b 6-month safety reports will be provided with the PSUR submission (PSUR single assessment [PSUSA]) as determined by the EURD list.
- c Interim reports will be prepared at year 5, 10 and 15 after EC decision date or when last patient is out of the registry-based study.
- $^{d}$  15 years after reaching the defined patient number no further data will be included in the study analyses.

